11.3 MedDRA Search Strategy for GI TEAEs and Hepatobiliary TEAEs51

11.4 Visit Windows.....53

11.5 Schedule of Events.....54

List of Tables

Table 8.7.1: Biomarkers and LC-FAOD-related Laboratory Measures43

Table 8.7.2: Clinical Laboratory Assessments44

Table 8.7.3: Screen for Liver/Muscle Damage45

Table 11.1.1: Summary Table of UX007-CL202 Efficacy Endpoints and Analysis.....49

Table 11.2.1: CTCAE Severity Grades for Selected Laboratory Parameters50

Table 11.3.1: Hepatobiliary Disorders51

Table 11.4.1: Visit Time Windows53

Table 11.5.1: Schedule of Events54

List of Figures

Figure 3.1: UX007-CL202 Study Schema14

Figure 5.9.3.1: Diagram of Study Periods in CL20222

LIST OF ABBREVIATIONS

AE	adverse event
ALT	alanine aminotransferase
AST	aspartate transaminase
BHB	beta-hydroxypentanoate
BHP	beta-hydroxybutyrate
CDC	Centers for Disease Control and Prevention
CK	creatinine kinase
CTCAE	common terminology criteria for adverse events
ECHO	echocardiogram
ICF	informed consent form
LC-FAOD	long-chain fatty acid oxidation disorders
LLN	lower limit of normal
MCE	major clinical event
MCS	mental health component summary score
MedDRA	Medical Dictionary for Regulatory Activity
OHSU	Oregon Health & Science University
PCS	physical health component summary score
PDMS-2	Peabody Developmental Motor Scales 2nd edition
PEDI-CAT	Pediatric Evaluation of Disability Inventory Computer Adaptive Test
PK	pharmacokinetics
PT	preferred term
SAE	serious adverse event
SAP	statistical analysis plan
SDTM	study data tabulation model
SF	shortening fraction
SF-10	Medical Outcome Study 10-items Short Form for Children
SF-12	Medical Outcome Study 10-items Short Form
SI	Le Système International d'Unités (International System of Units)
SMQ	standardized MedDRA query
SOC	system organ class
TEAE	treatment-emergent adverse event
ULN	upper limit of normal

1 INTRODUCTION

The purpose of this Statistical Analysis Plan (SAP) is to provide details of the statistical analyses that have been outlined within the UX007-CL202 original protocol and all amendments through Protocol Amendment 6 dated 01 October, 2019. This is the original version of SAP for this study. Changes from these guidelines must be substantiated by sound statistical reasoning and documented in the clinical study report (CSR).

Should there be a difference between the SAP and the protocol with respect to data analysis, the SAP will take precedence over the protocol.

2 STUDY OBJECTIVE(S)

2.1 Primary Objective(s)

The primary objective of the study is to:

- Evaluate the long-term safety and efficacy of UX007 in LC-FAOD subjects

2.2 Secondary Objective(s)

The secondary objectives of the study are to:

- Evaluate the effect of UX007 on energy metabolism in LC-FAOD
- Evaluate impact of UX007 on clinical events associated with LC-FAOD

[figure not shown]
3 STUDY DESIGN

The study is an interventional, open-label, long-term safety and efficacy extension study of UX007 treatment in approximately 100 LC-FAOD subjects who have participated in prior clinical studies or treatment programs with UX007/triheptanoin or are treatment naïve (i.e., naïve to both UX007 and food-grade triheptanoin), have failed conventional therapy, and have severe unmet need.

Following the signing of informed consent at the baseline visit, subjects will complete required assessments and return for clinic visits at 6 month intervals (± 2 weeks) to assess long-term safety and efficacy. There will be periodic phone calls at specified intervals (± 1 week) for additional safety monitoring. The subjects will be followed to evaluate the long-term safety and continued effects of UX007 for approximately 7 years or until market approval, whichever occurs first. A Safety Followup- Phone Call will be conducted 30-35 days after last dose of study drug. The last subject's Safety Follow-up Phone Call is the End-of-study Time Point.

The following figure provides a schematic of the study design.

Figure 3.1: UX007-CL202 Study Schema

Biologic and clinical assessments will be conducted throughout the 84 month Treatment Period. Clinical efficacy measures, biomarkers and LC-FAOD laboratory measures, PK measurements, and safety measures will be collected per the schedule of assessment in Appendix 11.5. The occurrence of major LC-FAOD clinical events will be captured at each visit (clinic or phone) through early termination visit. Dosing compliance and diet will be regularly monitored along with a standard panel of safety assessments.

A PK sub-study will evaluate the steady-state PK of UX007 and UX007 metabolites in a minimum of 12 subjects with LC-FAOD. Subjects enrolled in the sub-study will have serial PK samples collected.

3.1 Study Population

The study is designed to obtain long-term safety information and evaluate maintenance of efficacy in a diverse LC-FAOD population.

The study will be conducted in approximately 100 subjects who have participated in clinical studies or compassionate use programs with UX007/triheptanoin, or who have failed conventional therapy and have documented severe unmet need (in the opinion of the investigator and sponsor). Most subjects in this study will have prior treatment exposure to UX007/triheptanoin, although it is possible to enroll treatment-naïve individuals if prior study participation involved assignment to a control treatment arm.

The inclusion criteria are structured to enroll subjects with various types of LC-FAOD (CPT-I, CPT-II, VLCAD, LCHAD, TFP, or CACT deficiencies). Refer to the protocol for detailed inclusion and exclusion criteria.

Subjects in this study are to meet one or more of the following requirements:

- Participated in the UX007-CL201 study (ClinicalTrials.gov Identifier: NCT01886378)
- Previously enrolled in another UX007/triheptanoin study.
 - Study Sponsors/Collaborators include: Oregon Health & Science University (referenced as OHSU)
 - University of Pittsburgh (referenced as CompUse; ClinicalTrials.gov Identifiers: NCT01379625 and NCT01461304).
 - Participated in the UX007-CL001 study
 - Received UX007/triheptanoin treatment as part of other clinical studies; investigator sponsored trials (IST); expanded access/compassionate use treatment programs; eIND.
- Are treatment naïve (i.e., naïve to both UX007 and food-grade triheptanoin), have failed conventional therapy and, in the opinion of the investigator and sponsor, have documented severe unmet need, may also be eligible at the discretion of the sponsor.

3.2 Dosage and Administration

The UX007 investigational product, triheptanoin, will be administered orally with food or by gastronomy tube (usually four times per day: breakfast, lunch, dinner, and before bed), at the target dose range of 25-35% of total calories. If a subject has been receiving a lower dose of triheptanoin, the individual may continue treatment at the current dose provided there is no evidence of symptomatic disease or clinical signs of exercise limitation. UX007 doses above 35% of total caloric intake may be considered as needed at the discretion of the Investigator on an individual basis; it is recommended that doses above 35% are discussed with the Medical Monitor prior to administration.

3.3 Study Duration

Subject participation duration in this extension study will be up to 7 years (84 months) or until market approval, whichever occurs first. The total UX007 treatment duration per subject will vary depending on prior exposure from participation in clinical studies and compassionate use programs. The 7-year study duration will provide a continued treatment option and enable a long-term assessment of the safety and efficacy of UX007 in subjects with LC-FAOD under a single study protocol. A safety follow-up phone call will be conducted 30-35 days after last dose of study drug. The last subject's safety follow-up phone call is the end-of-study time point.

3.4 Blinding and Randomization Methods

Since this is a single-arm open label study, hence randomization and blinding are not applicable.

3.5 Stratification Factors

There is no randomization and thus no stratification factors.

3.6 Sample Size Considerations

Approximately 100 subjects with a history of participation in a UX007/triheptanoin clinical study, or who have failed conventional therapy and have documented severe unmet need (in the opinion of the investigator and sponsor) may be enrolled for this study. The sample size is intended to provide the maximum amount of information regarding UX007 long-term safety, along with indicators of sustained efficacy and durability of response.

A minimum of 12 subjects will participate in the PK sub-study at selected sites.

3.7 Interim Analysis

No formal interim analysis is planned for this study. Additional administrative analysis might be done at sponsor's discretion to support regulatory submission or product planning.

3.8 Data Monitoring Committee

There is no formal data monitoring committee planned for this study. Conduct of the study and safety of the subjects will be monitored by Ultragenyx on a regular basis.

3.9 Discussion of Study Design, Including Choice of Control Group

For subjects who previously participated in the UX007-CL201 study or were treatment naïve, historical major clinical events data will be collected for the 18-24 months prior to beginning UX007 (or from birth for subjects less than 18 months of age), enabling those subjects to represent an internal control for assessment of efficacy.

4 STUDY ENDPOINTS AND COVARIATES

All data are collected according to the schedule of assessments (Appendix 11.5). This section details the definition of each study endpoint. Table 11.1.1 in Appendix 11.1 provides a summary of efficacy endpoints and the statistical method for each efficacy endpoint.

4.1 Primary Efficacy Endpoint

The primary efficacy endpoint is:

- The annualized LC-FAOD major events rate inclusive of skeletal myopathy (rhabdomyolysis), hepatic (hypoglycemia) and cardiomyopathy events.

The primary efficacy endpoint is also referred as annualized major clinical event (MCE) rate. Section 5.1 defines what constitute an MCE and Section 5.11 presents the mathematical formula for deriving an annualized event rate.

4.2 Secondary Efficacy Endpoints

- Cardiomyopathy and cardiac function endpoints as measured by Echocardiogram (ECHO):
 - Ventricle size
 - Ejection fraction (EF)
 - Shortening fraction (SF)
- Annualized duration rate of all MCEs, where duration is defined as the total duration in number of days of MCEs
- Number and duration of each type of MCE (i.e., rhabdomyolysis, cardiomyopathy, and hypoglycemic events):
 - Annualized event rate of rhabdomyolysis MCEs
 - Annualized duration rate of rhabdomyolysis MCEs
 - Annualized event rate of cardiomyopathy MCEs
 - Annualized duration rate of cardiomyopathy MCEs
 - Annualized event rate of hypoglycemic MCEs
 - Annualized duration rate of hypoglycemic MCEs

4.3 Exploratory Endpoints

Exploratory endpoints include the following:

- Functional disability and cognitive development endpoints based on the Medical Outcomes Study 10-Item Short Form for Children (SF-10) or the Medical Outcomes Study 12-Item Short Form (SF-12) (instrument selection based on age):
 - SF-10 physical health component summary (PCS) score
 - SF-10 mental health component summary (MCS) score
 - SF-12 physical health component summary (PCS) score
 - SF-12 mental health component summary (MCS) score
- Clinical biomarkers endpoints as measured by:
 - Serum creatinine kinase
 - Fasting serum glucose
 - Alanine aminotransferase (ALT)
 - Aspartate transaminase (AST)
 - Gamma glutamyl transpeptidase (GGT)
- Growth measurements:
 - Height
 - Weight
 - Head circumference, if applicable (subjects \leq 36 months of age)

Additional endpoints were collected during earlier versions of the protocol and were later removed from the protocol amendments. These endpoints are listed below.

- Peabody Developmental Motor Scales 2nd edition (PDMS-2) for children under age 6 and children over age 6 that are unable to perform a valid and consistent cycle ergometry test or 12MWT (removed from Amendment 1)
- 12 Minute Walk Test (12MWT) (removed from Amendment 4)
- The Pediatric Evaluation of Disability Inventory Computer Adaptive Test (PEDI-CAT) for all subjects under the age of 18 (or for subjects 18- 20 years as clinically indicated) at the time of informed consent (removed from Amendment 4)

- Subject diary (removed from Amendment 4)

Data available for the above additional endpoints will be included in listings as collected.

4.4 Safety Endpoints

Safety events will be collected as adverse events (AE) or serious adverse events (SAE).

Primary safety endpoints are incidence and severity of treatment emergent AEs

The other safety endpoints in this study are:

- Vital signs
- Incidence of laboratory abnormalities
- Concomitant medications

4.5 Pharmacokinetics Endpoints

PK endpoints for this study include:

- Plasma levels of UX007
- Plasma levels of UX007 metabolites, including heptanoate, beta-hydroxypentanoate (BHP), and beta-hydroxybutyrate (BHB)

4.6 Potential Covariate(s)

No covariates are planned for use in the analysis of primary and secondary efficacy endpoints.

5 DEFINITIONS

5.1 Pharmacokinetic Objectives

- Characterize the steady-state pharmacokinetics (PK) of UX007 and UX007 metabolites in subjects with LC-FAOD

5.2 MCE

Major clinical events (MCE) include skeletal myopathy (rhabdomyolysis), hepatic (hypoglycemia) and cardiac disease (cardiomyopathy) events, and are defined as any visit to the ER/acute care, hospitalization, emergency intervention (i.e. any unscheduled administration of therapeutics at home or in the clinic), or any similar event whether caused primarily by LC-FAOD or by an intercurrent illness complicated by LC-FAOD.

5.3 Study Day 1

For all subjects, study day 1 is defined as the day of the first UX007 dose during Study UX007-CL202. For subjects who previously participated in study UX007-CL201, study day 1 coincides with the last UX007-CL201 visit.

Study Day 1 will be used to calculate the study days for all listings.

5.4 UX007 Treatment Day 1

UX007 treatment day 1 is defined as the day of the first UX007 dose. For subjects who rolled over from UX007-CL201, UX007 treatment day 1 is the day of the first UX007 dose during the UX007-CL201 study. For subjects who were UX007/trihep naïve, UX007 treatment day 1 coincides with study day 1.

UX007 treatment day 1 will be used to calculate days on UX007 for subjects who rolled over from UX007-CL201 and for naïve subjects in select statistical analyses.

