Clinical laboratory data will be summarized by the type of laboratory test. The frequency and percentage of subjects who experience abnormal clinical laboratory results (i.e. outside reference ranges) and/or clinically significant abnormalities will be presented for each measurement.

	Base	eline ¹	Treatment Extension ² Year 1				Treatment Extension ² Years 2-7			Early- Term/End of Study ³	Safety Follow-up (30-35 days) ¹³
Month	0	0.5	3	6	9	12	15, 21, 27, 33, 39, 45, 51, 57, 63, 69, 75, 81	18, 30, 42, 54, 66, 78	24, 36, 48, 60, 72, 84		
Түре	Clinic	Phone	Phone	Clinic	Phone	Clinic	Phone	Clinic	Clinic	Clinic	Phone
Informed Consent ¹	X										
Medical & Triheptanoin Treatment History ⁴	Х										
Growth ⁵	X			X		Х		Х	Х	Х	
SF10/12	X			X		Х		Х	Х	Х	
Echocardiogram (ECHO) ⁶	X					X			X	Х	
LC-FAOD Major Events Assessment ⁷	X	Х	X	X	X	X	Х	Х	X	Х	
LC-FAOD Biomarkers & Laboratory Measures ⁸	X			X		X		X	X	Х	
Vital Signs ⁹	X			Х		Х		Х	X	Х	
Physical Examination	X			Х		Х		Х	Х	Х	
Clinical Laboratory Tests ¹⁰	X			Х		Х		Х	X	Х	
Urine Pregnancy Test	X			Х		Х		Х	X	Х	
Adverse Events	Х	Х	Х	Х	Х	Х	Х	Х	Х	Х	X
Concomitant Medications	Х	Х	Х	X	Х	Х	Х	X	X	Х	Х

Table 2.1: Schedule of Events

	Baseline ¹		Treatment Extension ² Year 1			Treatment Extension ² Years 2-7			Early- Term/End of Study ³	Safety Follow-up (30-35 days) ¹³	
Month	0	0.5	3	6	9	12	15, 21, 27, 33, 39, 45, 51, 57, 63, 69, 75, 81	18, 30, 42, 54, 66, 78	24, 36, 48, 60, 72, 84		
Түре	Clinic	Phone	Phone	Clinic	Phone	Clinic	Phone	Clinic	Clinic	Clinic	Phone
Dietary Assessment and Diet diary ¹¹				Х		Х		Х	Х	Х	
UX007 Treatment & Compliance ¹²	X	Х	Х	X	X	X	Х	Х	X ¹²	X ¹²	
Plasma UX007 and Metabolites ¹⁴				X ¹⁴		X ¹⁴		X ¹⁴	X ¹⁴		
Standardized Meal ¹⁴				X ¹⁴		X ¹⁴		X ¹⁴	X ¹⁴		

¹ The Baseline visit may occur in conjunction with the last scheduled visit from study UX007-CL201. Assessments conducted at the last UX007-CL201 visit will be used for Baseline data to avoid duplication. Minor subjects who turn 18, should provide consent at their next visit.

² Clinic Visits will occur at 6 month intervals (± 2 weeks). The window for phone visits is ± 1 week.

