7.3.1 Inclusion Criteria

Individuals eligible to participate in this study must meet all of the following criteria:

- 1. Male or female, 6 months of age or older
- 2. Prior participation in a clinical study assessing UX007/triheptanoin treatment for LC-FAOD. Study Sponsors/Collaborators include: Oregon Health & Science University, University of Pittsburgh, and Ultragenyx Pharmaceutical (ClinicalTrials.gov Identifiers: NCT01379625, NCT01461304, and NCT01886378). Patients who received UX007/triheptanoin treatment as part of other clinical studies; investigator sponsored trials (IST); expanded access/compassionate use treatment programs; or patients who are treatment naïve (i.e., naïve to both UX007 and food-grade triheptanoin), have failed conventional therapy and, in the opinion of the Investigator and Sponsor, have documented clear unmet need, may also be eligible at the discretion of the Sponsor.
- 3. Confirmed diagnosis of LC-FAOD including: carnitine palmitoyltransferase (CPT I or CPT II) deficiency, very long chain acyl-CoA dehydrogenase (VLCAD) deficiency, long chain 3-hydroxy-acyl-CoA dehydrogenase (LCHAD) deficiency, trifunctional protein (TFP) deficiency, or carnitine-acylcarnitine translocase (CACT) deficiency. Information

on diagnosis will be obtained from medical records and should include confirmed diagnosis by results of acylcarnitine profiles, fatty acid oxidation probe studies in cultured fibroblasts, and/or mutation analysis.

- 4. Willing and able to complete all aspects of the study through the end of the study, including visits and tests, documentation of symptoms and diet, and administration of study medications. If a minor, have a caregiver(s) willing and able to assist in all applicable study requirements.
- 5. Provide written informed consent (subjects aged ≥ 18 years), or provide written assent (where appropriate) and have a legally authorized representative willing and able to provide written informed consent, after the nature of the study has been explained and prior to any research-related procedures.

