5.6 Subject Cohorts for Presentation

All CL202 subjects will be classified into one of the three non-overlapping cohorts in analysis presentations:

- UX007/trihep naïve subjects. This cohort consists of subjects who had no prior exposure to UX007/trihep before enrolling into CL202. However if a subject participated in a prior UX007/trihep study but was off UX007/trihep for more than two years before enrolling into this study, then this subject will be treated as a naïve subject and historical major clinical events will be collected.
- UX007-CL201 rollover subjects. This cohort consists of subjects who rolled over from UX007-CL201 to UX007-CL202 study.
- Other. This cohort includes subjects unassigned to the above two cohorts, i.e., subjects from [name] Comp sites, OHSU site, eIND program and etc.

A subject may have participated in more than one prior UX007/trihep studies/programs, and the cohort that the subject will be assigned to is determined based on the following priority order: UX007-CL201 rollover subjects and Other.

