5.11 Annualized Event Rate

The numbers of MCE will be annualized for each subject using the following formula:

$$\text{Annualized Event Rate} = \frac{\text{Number of events}}{\text{Duration of data collection period in days}/365.25}$$

The number of MCEs will be derived as the total number of events as recorded in the major clinical event CRF that occurred during the specific data collection period. Whenever an annualized rate is calculated over study period 1, the number of days is calculated from study day 1 till the data cutoff date or the early termination/study completion visit date for subjects who have early terminated/completed the study.

Annualized event rates will be calculated for MCEs overall and for each event type (ie., rhabdomyolysis, hypoglycemia, and cardiomyopathy respectively).

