8.5.5.3 Analyses of Non-MCE endpoints in CL201-Rollover Cohorts

The following efficacy endpoints will be analyzed for this analysis:

- ECHO variables: Ventricle size, EF, and SF
- Growth measurements

In these analyses, baseline will be shifted to the UX007 treatment baseline. Scheduled visits in UX007-CL201 will be converted to months and then aligned with UX007-CL202 visits. For example, Week 24 visit in UX007-CL201 is mapped to Month 5.5 visit. Assessments taken during the UX007-CL202 baseline visit or the last scheduled visit from study UX007-CL201 are mapped to Month 18 visit. For other visits in UX007-CL202, 18 months will be added to the visit number. For example, Month 6 visit in UX007-CL202 is mapped to Month 24 visit.

Summary statistics will be presented for ECHO variables (ventricle size, EF, and SF) and corresponding changes from UX007 treatment baseline by visit.

The same analysis methodology as described in Section 8.5.3.3 will be adopted for these integrated analyses of growth measurements.

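### SAP 5.3 gives two definitions of study day 1, which conflict for any prior CL201 participant whose first CL202 dose is not on the day of the last CL201 visit

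*SAP*

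**What the plan says.** SAP 5.3 contains two statements:

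- The general rule: "For all subjects, study day 1 is defined as the day of the first UX007 dose during Study UX007-CL202".
- A sentence on prior CL201 participants: "For subjects who previously participated in study UX007-CL201, study day 1 coincides with the last UX007-CL201 visit".

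Study day 1 then feeds several derivations:

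- It opens study period 1, the main analysis period (SAP 5.10.1).
- It starts the denominator of the annualized MCE rate, where "the number of days is calculated from study day 1 till the data cutoff date" or to the termination or completion visit (SAP 5.11). The duration rate uses the same denominator (SAP 5.12).
- It starts adverse event observation time (SAP 5.21).
- It fixes baseline, which is the last valid assessment on or before that day (SAP 5.7).
- For naïve subjects it also equals UX007 treatment day 1 (SAP 5.4), which separates the pre-treatment from the post-treatment window.

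On the timing of entry into CL202:

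- Inclusion criterion 2 asks for "Prior participation in a clinical study assessing UX007/triheptanoin treatment for LC-FAOD" and gives no maximum interval (Protocol 7.3.1).
- Table 2.1, footnote 1, says: "The Baseline visit may occur in conjunction with the last scheduled visit from study UX007-CL201". This permits a joint visit but does not require one.
- Protocol 7.4.4 provides for subjects who have been off treatment for more than a month.
- SAP 5.6 provides for a prior-study participant who "was off UX007/trihep for more than two years before enrolling into this study". Such a subject is handled as naïve, and historical MCEs are collected.

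**The concern.** The second sentence refers to anyone who took part in CL201, not only to those who rolled over on the same day. A programmer may reasonably let the specific sentence govern over the general one. For a subject with a gap, study period 1 would then start before CL202 consent.

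Three things follow:

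- **Event rates.** The denominator gains days on which CL202 was not following the subject. Adverse events are recorded only from consent (Protocol 7.5.5.7), and events carried over from CL201 are excluded by reference to the first CL202 dose (SAP 8.7.1). The numerator and denominator of the adverse event rate would therefore start on different dates. For MCEs, capture in the gap is not assured. The bias lowers the rates, which favours the drug.
- **Baseline.** Assessments at the CL202 Baseline visit would fall after study day 1, so an older CL201 value would take their place. This applies to the echocardiogram, which Protocol 7.5.2.2 requires at that visit. The rationale for Amendment 2 puts the last CL201 echocardiogram at week 24.
- **The naïve-cohort comparison.** If a prior CL201 subject is classed as naïve, the misplaced day 1 moves both windows of the paired pre/post test in SAP 8.5.4.1.

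**Working it through.** The documents give no rate, event count or power figure that depends on study day 1, so there is no stated figure to reproduce. The size follows from the formula in SAP 5.11.

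**1. One subject's rate.** The formula is rate = events / (days / 365.25). Let f be follow-up from the first CL202 dose and g the time from the last CL201 visit to that dose. If no events are captured in the gap, the reported rate divided by the rate over f is f / (f + g). The values of g are assumed, because the documents give none.

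| f (months) | g = 0 | g = 1 | g = 6 | g = 12 |
|---|---|---|---|---|
| 18 | 1.00 | 18/19 = 0.95 | 18/24 = 0.75 | 18/30 = 0.60 |
| 36 | 1.00 | 36/37 = 0.97 | 36/42 = 0.86 | 36/48 = 0.75 |
| 84 | 1.00 | 84/85 = 0.99 | 84/90 = 0.93 | 84/96 = 0.88 |

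For illustration, 3 events in 18 months is 3/1.5 = 2.0 per year. With a 6-month gap in the denominator it becomes 3/2.0 = 1.5 per year. If some gap events are captured, the factor lies closer to 1.

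**2. The first 18-month interval (SAP 8.5.1).** Here the gap takes up part of a fixed window, so the factor is (18 − g)/18 under an even event rate: 17/18 = 0.94 for 1 month and 12/18 = 0.67 for 6 months.

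**3. The cohort mean.** Let s be the share of rollover subjects with a gap, with equal true rates and f = 36 months. The mean rate is multiplied by 1 − s + s × 36/(36 + g). Both s and g are assumed:

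- s = 5%, g = 1: 0.95 + 0.05 × 0.973 = 0.999
- s = 10%, g = 6: 0.90 + 0.10 × 0.857 = 0.986
- s = 25%, g = 6: 0.75 + 0.25 × 0.857 = 0.964

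**4. The subject reclassified as naïve.** Take a CL201 completer who stopped drug at the last CL201 visit and enters CL202 more than two years later.

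- SAP 5.6 classes the subject as naïve, and SAP 5.4 equates treatment day 1 with study day 1.
- Under the second sentence of 5.3, both fall on the last CL201 visit.
- The post-treatment window is the next 18 months (548 days). The gap exceeds 730 days, so the whole window lies off drug.
- The pre-treatment window is the preceding 548 days (SAP 5.10.3). CL201 ran 24 + 54 = 78 weeks, or 546 days (Protocol, Section 5). Thus 546/548 = 99.6% of that window is CL201 treatment.

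Under the first sentence of 5.3, day 1 is the first CL202 dose. The factors in steps 1 to 3 are then all 1.00, and the windows in step 4 fall around the restart of treatment.

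**The case against.** The strongest reply is that the first sentence is the rule and the second only describes what happens in a seamless rollover. SAP 5.4 uses the same verb in that descriptive way for naïve subjects. Other text agrees: SAP 5.21 explains study day 1 as the first dose of UX007, and the rules for treatment-emergent events, gastrointestinal time to event, date imputation and concomitant medication all use the first dose in CL202. On that reading nothing is miscalculated. This stands as evidence of intent. It does not remove the second sentence, which as written covers every prior CL201 participant and contradicts the first wherever a gap exists.

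Three further replies also have force:

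- **No gap is shown.** The provisions for more than one month and more than two years off drug cover all prior programmes. Protocol Section 5 describes CL201 subjects as continuing treatment. Using last-visit CL201 values as baseline is the stated design when the visits are joint.
- **Missed MCEs are not established.** Table 2.1 schedules a major events assessment at Baseline with no stated look-back, and SAP 5.6 orders historical collection for subjects reclassified as naïve. Only adverse events before consent are clearly outside CL202 collection. Applying the dilution factor to a two-year gap would therefore be unsafe. The problem for those subjects is the misplaced windows.
- **The cohort effect is likely small.** The assumed cases above run from 0.1% to 3.6%, and the primary analysis is descriptive.

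A reader might infer that the plan fixes day 1 at the last CL201 visit for every prior CL201 participant, and that the reported rates are therefore too low. The documents support neither step, because the first sentence says otherwise and no gap subject is documented.

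**Conclusion.** SAP 5.3 contains an unresolved contradiction about the origin of the main analysis period. It has an effect only for a prior CL201 participant whose first CL202 dose is not on the day of the last CL201 visit. The protocol allows that situation, but the documents do not show that it occurred.

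If the second sentence is applied to such a subject, the MCE rate is multiplied by as little as f/(f + g). With 18 months of follow-up that is 0.95 for a 1-month gap and 0.75 for a 6-month gap, assuming that no events are captured in the gap. Adverse event observation time would include time before consent, and a CL201 value would serve as baseline. In the naïve reclassification case, the comparison would set an off-drug window against one spent largely on CL201 treatment. This last result assumes a CL201 completer who stopped drug at the last CL201 visit.

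The effect is zero for same-day rollovers, and zero for everyone if the first sentence is followed.

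**What to change.** In SAP 5.3, keep the first UX007 dose in CL202 as study day 1 for all subjects. Delete the second sentence, or limit it to subjects whose first CL202 dose is on the day of the last CL201 visit. Confirm that the derivations under 5.4, 5.7, 5.10.1, 5.11, 5.12 and 5.21 take their origin from this single date.

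The cost is one sentence and a check of one derivation. No result changes for same-day rollovers. If there are gap subjects, their rates would be higher than under the second sentence.

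Two related points lie outside the required change. SAP 8.5.5.3 carries the same no-gap assumption: "For other visits in UX007-CL202, 18 months will be added to the visit number". Aligning it is optional, since it affects only descriptive echocardiogram and growth summaries. Study period 2 runs from UX007 treatment day 1 to the end of CL202 (SAP 5.10.2), so for rollover subjects it contains any gap under either sentence, and this fix does not alter it.
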